4. ABSTRACT

Title: Patient profiles and treatment patterns among anaplastic lymphoma kinase (ALK)-positive non-small cell lung cancer (NSCLC) patients treated with alectinib.

Version and Date of Protocol: 2.0 31 August 2021

Main Author: PPD , PhD, Pfizer Inc; PPD , PhD, Ontada

Rationale and background:

Alectinib is a second-generation kinase inhibitor indicated for the treatment of patients with ALK+ metastatic NSCLC. Alectinib was first FDA approved in December 2015 for the treatment of ALK+ NSCLC in patients following treatment with the first generation ALK inhibitor crizotinib. In November of 2017, the FDA approved alectinib for use as first-line treatment for ALK+ metastatic NSCLC.

The approval was based on the Phase 3 ALEX trial of 303 first-line ALK+ NSCLC patients. Treatment with alectinib demonstrated a significantly reduced risk of progression or death by 47 percent (HR=0.53, 95 percent CI: 0.38, 0.73, p<0.0001) compared to crizotinib. Median PFS was 25.7 months (95 percent CI: 19.9, not estimable) for patients treated with alectinib compared with 10.4 months (95 percent CI: 7.7, 14.6) for patients who received crizotinib. Treatment with alectinib also reduced the risk of the brain or central nervous system (CNS) metastasis compared to crizotinib by 84 percent (HR=0.16, 95 percent CI: 0.10, 0.28, p<0.0001).[1]

With the availability of several therapeutic agents, current treatment patterns and outcomes with use of multiple ALK-inhibitor treatments in sequence are not well understood. For patients with ALK positive NSCLC, first-line therapy with alectinib is the preferred treatment option, however, sequence of therapy is not well-defined. This study aims to understand patient profiles, treatment patterns, and clinical outcomes among ALK+ NSCLC patients treated with alectinib, and post-alectinib treatment patterns and outcomes.

Research question and objectives

Describe patient profiles, treatment patterns, and clinical outcomes among real-world ALK+ NSCLC patients treated with alectinib, and post-alectinib treatment patterns and outcomes.

Specifically, we will answer the following objectives:

Phase 1: Landscape Objectives (structured data):

These analyses will be performed for all study-eligible patients who received alectinib (in any line of therapy) during the study identification period. Results will be presented overall as well as for the subgroups of patients who received a subsequent therapy following alectinib:

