9. RESEARCH METHODS

[figure not shown]
9.1. Study design Phases 1 and 2

This is a retrospective, observational, descriptive study to examine patient characteristics, treatment patterns, and outcomes of patients ALK+ NSCLC treated in The US Oncology Network and Non-Network practices utilizing the iKM EHR. During phases 1 and 2, patients who have evidence of receiving alectinib during 01 June 2017 and 30 June 2019 will be eligible for inclusion in the study.

Complete study eligibility criteria and cohort definitions are presented in Section 9.3. Study-eligible patients will be followed longitudinally until 31 December 2019, last patient record or date of death, whichever occurs first.

An overview of the study design for Phases 1 and 2 is presented below.

Figure 1. Phases 1 and 2 study design

^{*}last visit = last physical encounter; X = Additional visit or record of death

Phase 1 objectives will be assessed among patients who meet study eligibility criteria as specified in Section 9.3.1 and stratified by subsequent treatment following alectinib.

Phase 2 objectives will be assessed in a sample of patients who received alectinib as front-line therapy and stratified by subsequent treatment following alectinib.

The number of cohort stratifications may depend on sample size of patients receiving subsequent therapy following alectinib¹ including chemotherapy (further stratified into platinum doublet and single agent), immunotherapy, and ALK inhibitors. Up to 5 cohorts will be considered:

Cohort A: Patients who received alectinib during the study period (overall population)

Cohort B (alectinib only cohort): Patients with ongoing alectinib treatment, or patients who discontinued alectinib, and patients who did not have a subsequent treatment²

Cohort C: patients who received alectinib followed by treatment X (top 3 most frequent)

Cohort D: patients who received alectinib followed by treatment Y (top 3 most frequent)

Cohort E: patients who received alectinib followed by treatment Z (top 3 most frequent)

¹ Final cohorts will be decided upon sample size. Patients receiving chemotherapy and immunotherapy after initiating alectinib will be included in the patient sample. Chemotherapy cohort may be further stratified into platinum doublet chemotherapy and single agent chemotherapy depending on sample size.

[figure not shown]

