9.2. Study Design Phase 3 (study refresh and exploratory analysis)

During the Phase 3 data refresh, patients who have evidence of receiving alectinib during 01 June 2017 and 31 August 2020 will be eligible for inclusion in the study. Patients will be followed longitudinally until 31 August 2021, last patient record or date of death, whichever occurs first.

An overview of the study design for Phase 3 is presented in Figure 2.

Figure 2. Phase 3 data refresh study design

^{*}Last visit = last physical encounter, X = Additional visit or record of death

Phase 3 structured data objectives will be assessed among patients who meet study eligibility criteria as specified in 9.3.1 and stratified by subsequent treatment following alectinib.

Cohort A: All alectinib treated patients (overall population)

Cohort B (Alectinib only cohort): Alectinib treatment ongoing, or discontinued and no subsequent treatment³

Cohort C: Alectinib followed by treatment X (top 3 most frequent)

Cohort D: Alectinib followed by treatment Y (top 3 most frequent)

Cohort E: Alectinib followed by treatment Z (top 3 most frequent)

[figure not shown]
³ Patients with ongoing alectibin treatment, patients who discontinued alectinib and patients who did not have a subsequent treatment may be analyzed as separate cohorts depending on sample size of patients

Two groups of patients are planned for chart review during Phase 3. The first group includes patients from Phase 2 chart review who had ongoing treatment at the end of the observation period (31 December 2019). These patients will undergo additional follow-up through 31 August 2021.

An additional sample of approximately 100 patients who meet the Phase 3 eligibility criteria and received alectinib as front-line therapy and received subsequent treatment among the following groups will also undergo chart review:

- Alectinib → lorlatinib
- Alectinib → crizotinib
- Alectinib → brigatinib
- Alectinib only
- Alectinib → chemotherapy (optional)

Figure 3. Phase 3 exploratory analysis study design

^{*}Last visit = last physical encounter, X = Additional visit or record of death

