9.3. Setting

The study population will consist of patients with a diagnosis of NSCLC receiving alectinib within The US Oncology Network and Non-Network sites. The US Oncology Network includes approximately 1,400 affiliated physicians operating in over 480 sites of care across states and treats approximately 1.2 million US cancer patients annually. There are more than 2,650 active Non-Network supported oncology and non-oncology sites of care. [19]

Figure 1 and Figure 2 presents graphical depictions of the study time periods, which are as follows:

- Phase 1 and 2 study observation period: 01 June 2017 31 December 2019.
- Phase 1 and 2 study identification period: 01 June 2017 30 June 2019.
- Phase 3 study refresh observation period: 01 June 2017 31 August 2021.
- Phase 3 study refresh identification period: 01 June 2017 31 August 2020.
- Phase 3 exploratory analysis study observation period: 02 November 2018 31 August 2021.
- Phase 3 exploratory analysis study identification period: 02 November 2018 31 August 2020.
- Phase 1 and 2 index date-1: start date of alectinib treatment during the study identification period
- Phase 1 and 2 index date-2: start date of the subsequent treatment following alectinib, among patients who receive the next treatment during the study observation period
- Phase 3 study refresh index date-1: start date of alectinib treatment during the study identification period
- Phase 3 study refresh index date-2: start date of the subsequent treatment following alectinib, among patients who receive the next treatment during the study observation period
- Phase 3 exploratory analysis index date-1: start date of lorlatinib treatment during the study identification period
- Phase 3 exploratory analysis index date-2: start date of lorlatinib treatment among patients who receive next treatment during the study observation period
- Baseline: The baseline period or "at index" includes up to 30 days prior to and up to 30 days after index. If a patient has multiple baseline values for a particular demographic or clinical characteristic during this ± 30-day time frame, the one closest (in absolute value) prior to the index date will be used. If no values prior to index are available, then the one closest to the index date up to 30 days after will be used.

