- Prior medical history: Patients' available history in the iKnowMed (iKM) EHR will vary based on the length of disease and the time within The US Oncology Network. Disease characteristics such as time of NSCLC diagnosis and date of metastatic

disease will take into account patients' available medical history. The prior medical history period will end the day prior to the index date-1.

• Follow-up: Patients will be followed through the end of the study observation period, date of last visit or date of death, whichever occurs first. For analysis, patients will have a potential of at least 6 months of follow-up duration; however, patients will have variable follow-up time periods, depending on their index dates and last contact dates.

9.3.1. Phase 1 and 2 (original study) and Phase 3 (refresh study) population Inclusion criteria

Patients must meet all of the following inclusion criteria to be eligible for inclusion in the study:

- 1. Patients with a documented diagnosis of NSCLC.
- 2. Patients \geq 18 years of age at initial recorded diagnosis of NSCLC.
- 3. Patients who received treatment with alectinib within The US Oncology Network or Non-Network sites during the study identification period.
- 4. During the study observation period, patients observed with at least 2 visits⁴ after the index date-1.

Exclusion criteria

Patients meeting any of the following criteria will not be included in the study:

- 1. Receipt of treatment indicated for another primary cancer or diagnosis of another primary cancer (with the exception of non-melanotic skin cancer), within 5 years of index date-1 will be excluded.
- 2. Patients enrolled in clinical trials prior to receiving alectinib during the study ID period (index date-1), will be excluded.

⁴ Visits are defined as physical encounters with the practice, detected by vital sign records. The second and third visits must be observed after the index date-1 to demonstrate continuity of care. There is no required time span between the additional visits and the index date-1.

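### Eligibility turns on receiving alectinib in the identification period and index date-1 on starting it, so the protocol does not settle whether patients who started before 01 June 2017 are in the cohort

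*Combined protocol and SAP*

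**What the plan says.** **Entry.** Inclusion 3 in Section 9.3.1 takes "Patients who received treatment with alectinib within The US Oncology Network or Non-Network sites during the study identification period". Section 9.1 says of Phases 1 and 2 that "patients who have evidence of receiving alectinib during 01 June 2017 and 30 June 2019 will be eligible for inclusion in the study". Section 9.2 says of Phase 3 that "patients who have evidence of receiving alectinib during 01 June 2017 and 31 August 2020 will be eligible for inclusion in the study". The study population paragraphs of the abstract use the same idea of receipt. In the text that can be read, nothing asks for a first start, bars earlier alectinib or sets a washout.

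**Index.** Index date-1 in Section 9.3 and at the head of Table 1 is the "start date of alectinib treatment during the study identification period". Exclusion 2 in Section 9.3.1 describes it differently: "Patients enrolled in clinical trials prior to receiving alectinib during the study ID period (index date-1), will be excluded".

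**Calendar.** The abstract and Section 7 state that "Alectinib was first FDA approved in December 2015", for use after crizotinib; first-line approval followed in November 2017. The identification and observation periods open on the same day, as in "Phase 3 study refresh observation period: 01 June 2017 31 August 2021".

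**Analysis.** Section 9.8.3 runs OS from alectinib start and DOT from alectinib initiation, while the printed DOT formula subtracts the index date. The methods are ordinary Kaplan-Meier and log-rank, without delayed entry. Section 9.8 says that no separate analysis plan will follow. The limitations in Section 9.10 do not mention patients already on drug when the window opens.

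**The concern.** A patient who began alectinib in 2016 and was still taking it in June 2017 meets inclusion 3 as written. Whether that patient is analysed, and from which date, is left to whoever builds the dataset. Two programmers could build different cohorts from the same text, and no later document is planned to settle the matter.

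If such patients enter, both ways of handling them do harm.

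- **True start kept.** The patient is in the data only because treatment lasted until 01 June 2017. Patients who started at the same time and stopped earlier never appear. Counting the time before the window as ordinary follow-up overstates DOT and OS.
- **Index reset to the first in-window record.** The start date is false, part of the treatment course is lost, and the 30-day baseline window falls in mid-treatment.

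Because the stated approval before November 2017 was for use after crizotinib, these patients should sit mainly in the non-front-line group. Section 9.8.3 plans results by front-line status, if numbers allow, and names that split as an example of a comparison tested at the 0.05 level. The distortion would then fall unequally on the two strata.

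**Working it through.** The protocol states no figure to reproduce here, so the check has a textual part and an illustration of size.

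**1. The rules applied to one patient (start in 2016, still treated in June 2017).**

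- Inclusion 3 and Sections 9.1 and 9.2: eligible, because alectinib was received in the window.
- Index date-1, read strictly: no start falls in the window, so there is no index date. Inclusion 4, which counts visits after index date-1, cannot be met.
- Exclusion 2: in-window receipt is itself labelled index date-1, so the patient has one.

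The three do not agree.

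**2. Share of the cohort that could be affected.** Inputs from the documents, with months as days/30.4375:

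- pre-window span, counted from 1 December 2015 to 01 June 2017: 548 days, 18.0 months
- identification period *L*, Phases 1 and 2: 759 days, 24.9 months; Phase 3: 1,187 days, 39.0 months

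Assumptions not in the documents: exponential time on alectinib with median *m*; uniform starts; pre-window start rate *r* times the in-window rate. The upper value of *m*, 25.7 months, is the first-line trial median PFS cited in Section 7. The values 8, 12 and 18 months are plain assumptions.

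Fraction of pre-window starters still on drug: *s* = (1 − e^(−k))/k, with k = ln 2 × 18/*m*. Share of cohort = 18*rs*/(18*rs* + *L*).

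Low end: *m* = 8 gives k = 1.560 and *s* = 0.506. With *r* = 0.25, 18*rs* = 2.28, and 2.28/(2.28 + 24.94) = 8.4%.

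High end: *m* = 25.7 gives k = 0.485 and *s* = 0.792. With *r* = 1, 18*rs* = 14.26, and 14.26/(14.26 + 24.94) = 36.4%.

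| *m* (months) | *s* | Phases 1 and 2, *r* = 0.25 / 0.5 / 1 | Phase 3, *r* = 0.25 / 0.5 / 1 |
|---|---|---|---|
| 8 | 0.51 | 8.4% / 15.5% / 26.8% | 5.5% / 10.5% / 18.9% |
| 12 | 0.62 | 10.1% / 18.3% / 31.0% | 6.7% / 12.5% / 22.3% |
| 18 | 0.72 | 11.5% / 20.7% / 34.2% | 7.7% / 14.3% / 25.0% |
| 25.7 | 0.79 | 12.5% / 22.2% / 36.4% | 8.4% / 15.5% / 26.8% |

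**3. True start kept, no delayed entry.** This was simulated under the same assumptions, with 400,000 starts per scenario. Ranges run over *r* = 0.25 to 1.

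| True median DOT | Estimated, Phases 1 and 2 | Estimated, Phase 3 |
|---|---|---|
| 8.0 | 8.6 to 10.1 | 8.4 to 9.4 |
| 12.0 | 13.0 to 15.1 | 12.6 to 14.1 |
| 18.0 | 19.3 to 21.4 | 18.8 to 20.4 |
| 25.7 | 27.0 to 29.2 | 26.6 to 28.3 |

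The overstatement runs from 0.4 months (8.4 − 8.0) to 3.5 months (29.2 − 25.7). With *m* = 12 and *r* = 1 in Phases 1 and 2, the 12-month on-treatment probability is estimated at 0.584 against a true 0.500.

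For OS, survival was simulated as time on drug plus an exponential time after it, in six Phase 3 scenarios (medians 12 and 12, 18 and 12, 25.7 and 24 months; *r* = 0.5 or 1). Median OS rose by between 1.2 months (29.0 to 30.2) and 4.2 months (60.3 to 64.5).

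**4. Index reset.** Mean alectinib time lost per affected patient is 1/λ − 18e^(−k)/(1 − e^(−k)), with λ = ln 2/*m*. For *m* = 12 this is 17.31 − 9.85 = 7.5 months. For *m* = 8, 18 and 25.7 it is 6.8, 8.0 and 8.3 months. With a constant hazard, time still to run has the same distribution as time from start, so the Kaplan-Meier median DOT does not move. Any shift depends on the shape of the hazard.

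**The case against.** The strongest reply is that index date-1 is defined as a start inside the window, and that inclusion 4, both exclusions, baseline and prior history all hang on it. On that reading an earlier starter simply falls out. The protocol also uses receipt loosely elsewhere: the lorlatinib objective speaks of patients initiating the drug, yet its inclusion criterion in Section 9.3.2 uses the same receipt wording. In addition, the Table 1 row on eligibility by study drug is broken in the text available, and the design figures are not shown.

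Much of this stands. The text permits earlier starters to enter but does not prove that they will, and a statement elsewhere in the table or figures cannot be excluded. The reply still does not close the point: the exclusion is nowhere stated in the readable text, inclusion 3 contradicts it, and exclusion 2 ties the index to receipt.

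A reader might infer three stronger claims that the documents do not support.

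- **That PFS is biased as well.** Progression dates come only from chart review, which is aimed at front-line patients. Earlier starters should be few among them.
- **That resetting the index necessarily shortens median DOT.** It does not under a constant hazard.
- **That the affected share is known.** Both driving inputs are assumed. The 25.7 months comes from first-line trial patients, whereas the labelled use before the window was after crizotinib.

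**Conclusion.** The concern holds as an unreconciled conflict between the eligibility rule and the index-date definition. It is a conflict that can bias results, not a demonstration that the cohort is contaminated. It matters mainly for OS and DOT in the structured data and for the non-front-line stratum.

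Under the stated assumptions, earlier starters would make up about 8% to 36% of Phases 1 and 2 and about 6% to 27% of Phase 3. With true start dates and no delayed entry, median DOT would be overstated by roughly 0.4 to 3.5 months, and median OS by about 1 to 4 months in the Phase 3 scenarios tried. These figures rest on exponential times, uniform starts and assumed start rates, and the real number cannot be derived from the documents. If the sponsor already meant new starters only, the bias is nil and only the wording is at fault. The lorlatinib analysis is much less exposed, because its window opens at about the November 2018 approval.

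**What to change.** Reword inclusion 3, and the parallel statements in the abstract, Section 9.1 and Section 9.2, to require a first recorded alectinib start date within the identification period and no earlier alectinib record in the available history. Verify this in the chart for patients under chart review. Align exclusion 2 with the same definition, and report the number excluded in the attrition counts that Section 9.8.3 already plans.

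Alternatively, keep earlier starters in the treatment-pattern tables only. If they are also to contribute to OS and DOT, use the true start date with delayed entry at 01 June 2017 and report their number. Delayed entry suits DOT well. For OS it is only approximate, since entry requires being still on alectinib and not merely alive, so restriction to new starters is cleaner.

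The cost is a few sentences of text and the loss of some patients, mainly non-front-line; at the upper end of the range above that loss would not be small. Section 9.10.1 says that care outside the Network is not captured, so some earlier starts will still be missed. The limitations section should say so.

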9.3.2. Phase 3 exploratory analysis study population

Inclusion criteria

Patients must meet all of the following inclusion criteria to be eligible for inclusion in the study:

- 1. Patients with a documented diagnosis of NSCLC.
- 2. Patients \geq 18 years of age at initial recorded diagnosis of NSCLC.
- 3. Patients who received treatment with lorlatinib within The US Oncology Network or Non-Network practices during the study identification period.
- 4. During the study observation period, patients observed with at least 2 visits⁴ after the index date-1.

Exclusion criteria

Patients meeting any of the following criteria will not be included in the study:

- 1. Receipt of treatment indicated for another primary cancer or diagnosis of another primary cancer (with the exception of non-melanotic skin cancer), within 5 years of index date-1 will be excluded.
- 2. Patients enrolled in clinical trials prior to receiving lorlatinib during the study ID period (index date-1) will be excluded.

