9.4. Variables

Table 1. Study variables and operational definitions

Main Study

Index date-1= start date of alectinib treatment during the study identification period

Index date-2= start date of the subsequent treatment following alectinib, among patients who receive a next treatment during the study identification period

Exploratory Analysis

Index date-1= start date of lorlatinib treatment during the study identification period

Index date-2= start date of the subsequent treatment following lorlatinib, among patients who receive a next treatment during the study observation period

Table 1. Study variables and operational definitions

Variable	Source(s)	Role(s) in study	Period of measurement	Operational definition
Demographic at	nd patient ch	aracteristics		
PatID	iKM structured data	Data linkage	Study observation period	Unique patient identifier that will be used to link clinical records. This information will not be disclosed to the study sponsor.
Medical record number (MRN)	iKM structured data	Data linkage	Study observation period	Unique patient identifier that will be used to link clinical records. This information will not be disclosed to the study sponsor.
Clinical trial participation	iKM structured data + chart review	Eligibility criteria	Follow-up	Patients enrolled in interventional clinical trials (patients in only observational studies will be retained, if applicable) in The US Oncology Network or Non-Network during the study observation period will be flagged.
Other cancer diagnosis	iKM structured data + chart review	Eligibility criteria	Prior medical history + study observation period	Patients will be confirmed as having no additional primary or secondary malignancies (with the exception of non-melanotic skin cancer) within the 5 years prior to and after the index date-1. Patients with a secondary diagnosis or receipt of treatment indicated for another primary cancer within 5 years prior to index date-1 will be excluded.
Additional visits	iKM structured data	Eligibility criteria	Follow-up	To capture a sample of patients with longitudinal records, patients will be required to have 2 records of either additional visits following the index date-1 visit and/or a record of death prior to the end of the study follow-up period. Visits are defined as physical encounters with the practice, detected by vital sign records. There will be no distinction made, for purposes of inclusion, between patients that have an

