9.8. Data analysis

As the foreseen analyses are defined in enough detail in this protocol, no further statistical analysis plan will be developed.

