9.8.3. Statistical methods

Description of study enrollment

To be included in the study patients must meet each of the inclusion criteria and none of the exclusion criteria listed in Section 9.3.1. Counts of patients excluded for each criterion will be summarized.

Additionally, the counts of patients to be classified into the following subgroups will be presented⁵:

- Cohort A: All alectinib treated patients (overall population)
- Cohort B (Alectinib only cohort): Alectinib treatment ongoing, or discontinued and no subsequent treatment⁶
- Cohort C: Alectinib followed by treatment X (top 3 most frequent)
- Cohort D: Alectinib followed by treatment Y (top 3 most frequent)
- Cohort E: Alectinib followed by treatment Z (top 3 most frequent)

Description of patient demographic, clinical and treatment characteristics

Descriptive analyses will be conducted to evaluate the demographic, clinical and treatment characteristics overall, as well as for each of the study cohorts. Results will be reported in

⁵ Final cohorts will be decided upon sample size. Patients receiving chemotherapy after initiating alectinib will be included in the patient sample

⁶ Patients with ongoing alectibin treatment, patients who discontinued alectinib and patients who did not have a subsequent treatment may be analyzed as separate cohorts depending on sample size of patients

aggregate. Categorical variables (e.g., ECOG performance status) will be reported as frequency and percentage. Continuous variables such as age will be reported as mean, standard deviation, median and range (minimum-maximum). In the case of missing observations, the number and percentage of missing values will be reported.

For comparative analysis, i.e. comparing 2 or more treatment groups (e.g., ALK inhibitor sequences) or strata (front-line alectinib and non front-line alectinib), statistical significance will be reported with level of statistical significance based on p = 0.05 level as well as 95% confidence intervals.

Chi-square testing will be used to assess associations between categorical variables when patient counts for single cells within the results tables are greater or equal to 5. When distribution cannot be assumed to be Chi-square, then Fisher's exact test will be used. Depending on normality, Analysis of variance (ANOVA)/t-tests or Kruskall-Wallis tests will be used for continuous variables. An alpha level of 0.05 will be the primary criterion for statistical significance of this study.

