All descriptive tables will be presented for each of the study cohorts defined above and, as supported by the final sample size, stratified by front-line alectinib and non front-line alectinib treatment groups.

For Phase 3 exploratory objectives, descriptive analyses will be conducted to evaluate the demographic, clinical and treatment characteristics among patients treated with lorlatinib. Results will be reported in aggregate. Categorical variables (e.g., ECOG performance status) will be reported as frequency and percentage. Continuous variables such as age will be reported as mean, standard deviation, median and range (minimum-maximum). In the case of missing observations, the number and percentage of missing values will be reported.

Clinical outcomes

ALK inhibitor DOT, OS, PFS will be assessed using the Kaplan-Meier method with 95% CIs, and summary tables of the number of events and censored patients at 3, 6, 12, 18, and 24 months. Further details about these calculations are presented below and in Table 1.

Clinical outcome results will be presented by study cohort and stratified by front-line alectinib and non-front line alectinib (pending sample size).

Overall survival (OS) will be defined as the interval between start date of alectinib to the date of death as documented in the LADMF and/or iKM EHR database. Patients who did not die will be censored on the study end date or the last visit date available in the database, whichever occurred first. In order to handle censoring, the Kaplan-Meier method will be used to calculate median overall survival with 95% confidence intervals (in number of months). Additionally, 3, 6, 12, 18, and 24-month survival probabilities will be reported. OS will be estimated for the full study population and stratified by study cohort. Log-rank tests will be used to assess statistical differences.

Duration of Therapy (DOT) for ALK inhibitors: An intent to treat approach will be used. DOT will be defined as duration of time (in months) between alectinib treatment initiation and discontinuation, or the last administration date of alectinib, or start date of a subsequent ALK inhibitor, initiation of any subsequent non-ALK inhibitor treatment (as a proxy for evidence of discontinuation), death or check-in in a hospice will be used as a stop date.

There may be some patients who do not have evidence of discontinuation or who do not move on to a subsequent therapy.

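### Section 9.3.1 requires two visits after alectinib start while Table 1 accepts a record of death; applied as written, 9.3.1 removes early deaths and inflates overall survival

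*Combined protocol and SAP*

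**What the plan says.** Criterion 4 in section 9.3.1, repeated for the lorlatinib cohort in 9.3.2, reads "During the study observation period, patients observed with at least 2 visits" after index date-1. Footnote 4 defines a visit as a physical encounter detected by vital signs and adds: "The second and third visits must be observed after the index date-1 to demonstrate continuity of care".

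The Additional visits row of Table 1 (section 9.4), whose stated role is eligibility, is different: "patients will be required to have 2 records of either additional visits following the index date-1 visit and/or a record of death". Its text then continues "There will be no distinction made, for purposes of inclusion, between patients that have an" additional visit and those with a death record. The legends of Figures 1 to 3 read "X = Additional visit or record of death".

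On which rule governs, section 9.8.3 says "patients must meet each of the inclusion criteria and none of the exclusion criteria listed in Section 9.3.1", sections 9.2, 9.3.3 and 9.8.1 also point to 9.3.1, and section 9.8 states that "no further statistical analysis plan will be developed".

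On the time origin, section 9.8.3 says "Overall survival (OS) will be defined as the interval between start date of alectinib to the date of death". PFS and DOT also start at alectinib initiation. No delayed entry is planned, and OS is reported at 3, 6, 12, 18 and 24 months.

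**The concern.** One population has two inclusion rules. Under criterion 4 as written, a patient who starts alectinib and dies before a second post-index visit is not in the study. Under Table 1, that patient may be.

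The choice matters because follow-up starts at alectinib initiation, before the qualifying visits. Requiring the visits means requiring survival past time zero (immortal time), so the visits-only reading raises OS, and the early landmarks are among those affected. PFS and DOT are affected less, and only through early deaths: a patient who progresses or stops early but attends twice stays in, with the event counted. The lorlatinib analysis has no survival objective, so there only the patient profile and sequencing would change.

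A reader could not see the problem in the report. Section 9.8.3 promises a count of patients excluded per criterion, but not how many of them died, and the limitations in section 9.10 do not mention it.

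**Working it through.** **Text.**

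| Place | Does a death record qualify? |
|---|---|
| 9.3.1 and 9.3.2, criterion 4 with footnote 4 | No: two vital-sign visits |
| Table 1, Additional visits | Yes, but two records are asked for |
| Figures 1–3, legends | Visit or death (figures not visible) |
| 9.8.1 and 9.8.3, analysed alectinib population | Refer to 9.3.1 |

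Table 1 is itself unclear. Two records could mean that a patient whose only post-index record is death does not qualify; its next sentence treats a visit and a death record alike.

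**Inputs.** The plan states no figure that rests on this criterion, so there is none to reproduce. From the documents: about 300 patients (Phase 1) and 521 (Phase 3 feasibility), section 4; median OS 6.8 years = 6.8 × 12 = 81.6 months from stage IV diagnosis, section 7. Assumed: visit spacing and early mortality.

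**Formula.** Let v be the time of the second post-index visit. If deaths before v are excluded, the excluded share is 1 − S(v), and for t > v the observed curve is S(t)/S(v). With constant hazard, S(t) = exp(−t·ln2/median). With share p dead by 3 months and a constant hazard afterwards, S(t) = (1 − p)·exp(−(t − 3)·ln2/median) for t ≥ 3.

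Example, median 81.6 months and v = 2 (monthly visits): S(2) = exp(−2 × 0.6931/81.6) = 0.983, so 1.7% are excluded; S(12) = 0.903 becomes 0.903/0.983 = 0.919.

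| Assumed death model | v (months) | Excluded | Of 300 / of 521 | 12-month OS, all → observed | Change (points) |
|---|---|---|---|---|---|
| Median 81.6 | 1 | 0.9% | 3 / 4 | 0.903 → 0.911 | +0.8 |
| Median 81.6 | 2 | 1.7% | 5 / 9 | 0.903 → 0.919 | +1.5 to +1.6 |
| Median 81.6 | 4 | 3.3% | 10 / 17 | 0.903 → 0.934 | +3.1 |
| 3% dead by month 3, then median 40 | 4 | 4.7% | 14 / 24 | 0.830 → 0.871 | +4.1 |
| Median 24 | 3 | 8.3% | 25 / 43 | 0.707 → 0.771 | +6.4 |
| 10% dead by month 3, then median 81.6 | 4 | 10.8% | 32 / 56 | 0.834 → 0.934 | +10 |
| 10% dead by month 3, then median 40 | 4 | 11.5% | 35 / 60 | 0.770 → 0.871 | +10 |

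**Variable visit times.** Simulation with 1,000,000 patients per scenario and three models for the gaps between visits (±25% jitter, gamma, exponential) gives:

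- Low case (median 81.6, monthly visits): 1.7% excluded; OS +1.6 points at 3 and 6 months, +1.5 to +1.6 at 12.
- 3% dead by 3 months, two-monthly visits: 4–5% excluded; +3.4 to +4.3 at 12 months.
- High case (10% dead by 3 months, two-monthly visits): 9–12% excluded; +8 to +10 at 3 months, +9 to +11 at 6, +8.5 to +10 at 12.

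**PFS and DOT.** If non-death events are independent of death, the OS change is multiplied by the probability of being free of a non-death event. With a non-death median of 20 or 38 months, that is 2^(−12/20) = 0.66 or 2^(−12/38) = 0.80 at 12 months. Simulated changes at 12 months (later median 81.6) are +1.0 to +1.2 points in the low case and +6.4 to +7.7 in the high case. With the 38-month value, median PFS moves from 25.9 to 26.5 months (low) and from 22.9 to 27.0 (high).

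**Readings of Table 1.** With median OS 24 months, a second visit averaging 2 months and no early loss, true 12-month OS is 0.707. Visits only gives 0.749, two records 0.727, and one death record sufficient 0.707. The two-record reading keeps about half the inflation: (0.727 − 0.707)/(0.749 − 0.707) = 0.48.

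**The case against.** The strongest reply is that Table 1 holds the operational definitions (sections 4 and 9.8.2) and addresses this very point, so it simply spells out criterion 4. That is a reasonable guess at intent, but no section gives Table 1 precedence, the analysed population is defined by 9.3.1, and Table 1 leaves the single-death case open.

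Several narrower points stand:

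- The figures are not visible, so their legends support Table 1 only by inference.
- The size is not anchored in the documents. The high case has no source, and the low case is not a floor (+0.8 points with v = 1). At the low-case hazard, the binomial 95% half-width for 12-month OS, ignoring censoring, is 1.96·√(0.903 × 0.097/n): about 3.3 points for n = 300 and 2.5 for n = 521. A bias of 1.5 points lies within that, although it does not shrink as n grows.
- The PFS medians are illustrative. The 38-month input was chosen to land near the 25.7 months cited in section 4, and that match is lost in the high case (22.9).
- Patients in Cohorts C to E lived to start a next treatment, so the effect falls mainly on Cohorts A and B. It can still disturb the planned log-rank comparisons, because Cohort B would lose its early deaths.
- The combined rule is not neutral: patients with few visits enter only if they die. With 5–10% leaving within 2 months, the low hazard and monthly visits, 12-month OS is 0.4 to 0.8 points below truth under that rule, against 1.4 to 1.5 above under visits only. Almost all of the shortfall also appears with no visit rule, because early leavers are censored while their deaths are still captured. The combined rule itself adds only 0.02 to 0.17 points.

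**Conclusion.** The concern holds. The two eligibility rules contradict each other and nothing in the plan chooses between them. If criterion 4 is followed as written, OS is biased upward, because inclusion then depends on surviving past time zero.

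The size is an assumption range: 1.7% of patients excluded and about +1.5 points on 12-month OS in the low case, 9–12% and +8.5 to +10 points in the high case, with 0.9% and +0.8 points possible if the second visit comes within a month. PFS and DOT move by about 65–80% of the OS change at 12 months. The 6.8-year median runs from diagnosis, whereas the structured analysis takes alectinib in any line, so the low case may understate the hazard. The contradiction and the direction are certain; the size is not. It should be settled before the Phase 3 extraction.

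**What to change.** Use one wording in 9.3.1, 9.3.2, footnote 4, Table 1 and the figures: 'at least 2 visits after index date-1, or a record of death after index date-1 (one death record is sufficient)'.

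In the attrition table, report how many patients enter through the death route and how many the visit rule excludes. If visits-only is kept instead, also report how many of those excluded died.

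Because the combined rule admits low-visit patients only if they die, add one sensitivity analysis of OS, PFS and DOT in the alectinib cohort, either without the visit rule or with risk time starting at the second post-index visit.

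The cost is a one-line change to the text and the extraction query plus one extra run. A few patients with sparse data will enter. If the Phase 1 and 2 reports used visits only, their figures will not match the new ones directly, but Phase 3 reruns those analyses and can apply one rule to all patients.
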